A blinded IR will assess the severity of PTSD symptoms at baseline, at the primary endpoint one month after the second experimental session, two months after the third open-label experimental session and at equivalent points in Stage 2. Cognitive function will be assessed at baseline, one month after the second experimental session and at two-month follow-up. All subjects will complete a long-term follow-up visit 12 months after their final experimental session in either Stage 1 or Stage 2. This study will provide an estimate of effect size based on dose response of PTSD symptoms to MDMA-assisted psychotherapy.

Two types of therapy teams will conduct psychotherapy visits according to the treatment manual [108]. Subjects will either be treated by teams consisting of two experienced co-therapists or teams consisting of an intern therapist paired with an experienced co-therapist. Information will be collected regarding consistency and response between the teams by reviewing adherence criteria in blinded videos of therapy sessions. This study will also continue the refinement of the treatment manual.

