5.1.3 Process Measures

All psychotherapy sessions, including experimental sessions, may be recorded to audio and video, with all recordings preserved for research and training purposes.

Adherence criteria and competence ratings will be conducted by qualified, trained blinded adherence raters who will analyze video data from selected preparatory, experimental and integrative sessions. The elements included in adherence criteria are specific to each type of session. These ratings will be collected, at minimum, for each therapist team in the study. The goal of these ratings will be to correlate therapist adherence to the treatment manual with outcome as a part of the sponsor’s ongoing efforts to standardize treatment methods of MDMA-assisted psychotherapy for PTSD.

The SOCQ is a 100-item questionnaire based on the “Peak Experience Profile” designed by Pahnke and colleagues [149, 150]. Subjects respond to the SOCQ using a six-point Likert-type scale anchored at 0=none at all and 5=extreme (more than ever before in my life). It has seven subscale scores; internal unity, external unity, transcendence of time and space, ineffability and paradoxicality (claim of difficulty in describing the experience in words), sense of sacredness, noetic quality, and deeply felt positive mood. The measure is a self-report instrument and takes approximately 20 to 30 minutes to complete. Subjects will complete the SOCQ after each experimental session, at any time between the end of an experimental session and prior to leaving the treatment facility the next day.

Questions regarding the belief of condition assignment and certainty of the belief will be asked of the therapists and subjects at the integrative session on the day after each blinded experimental session in Stage 1. Each therapist responsible for treating the subject will indicate their belief of condition assignment and certainty based on the active doses (125 mg or 100 mg) and comparator dose groups. In line with informed consent obfuscation, where the comparator dose is not revealed, subjects will initially be asked if they believe they received MDMA or not during this assessment. If they believe they received MDMA, they will be asked about what dose they think they received. These beliefs are collected as a part of the sponsor’s ongoing initiative to optimize the double-blind as a part of dose response studies.

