The sponsor will compare baseline and primary endpoint RBANS and PASAT scores in each active dose group and comparator dose groups. Active dose 1 and active dose 2 RBANS and PASAT data will be tested for equivalence using confidence intervals. If the two groups are found to be equivalent, then outcomes for the active dose groups will be combined and will be tested for significant differences from the comparator group using difference scores in independent sample t-tests, with p value set at 0.05. If scores for active dose 1 are not equivalent to active dose 2, then analysis of variance (ANOVA) will be used to compare outcomes from all three groups. The sponsor will examine the effects of maximal exposure to MDMA on neurocognitive function using the RBANS and PASAT by performing a within-subject repeated measures ANOVA with time of administration as a within-subjects factor.

The sponsor will collect ratings of adherence to the treatment manual from specifically selected types of sessions. Descriptive statistics will be computed for each adherence scale within a given session. The sponsor will explore the factors and structure of the measures of adherence to assist in further development of adherence and competence measures. If sufficient data is available, the sponsor will correlate the mean adherence ratings for adherence scale and session type with Global CAPS scores to investigate the effects of adherence to the treatment manual on reduction in PTSD symptoms. If it is found that there are specific factors within the adherence scales, then the factor will be correlated with Global CAPS score.

Subjects who discontinue treatment prior to the primary endpoint will be asked to complete an outcome assessment prior to continuing to the long-term follow-up. The data from these subjects will be tested for equivalence to data from subjects completing the study per protocol. If found to be equivalent, data from these subjects will be presented as an exploratory Intent-to-treat analysis to examine results without bias towards subjects more likely to complete the study per protocol, with last observation carried forward.

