4.2 Secondary Objectives

The following objectives will compare each active dose group and the comparator dose group in Stage 1:

- Assess changes in self-reported PTSD symptoms as measured with the PTSD Diagnostic Scale (PDS) at baseline, after each experimental session and/or the primary endpoint.
- Assess depression symptoms with the Beck Depression Inventory-II (BDI-II) at baseline and the primary endpoint.
- Assess global functioning with the Global Assessment of Functionality (GAF) at baseline and the primary endpoint.
- Assess self-reported sleep quality with the Pittsburgh Sleep Quality Index (PSQI) at baseline and the primary endpoint.
- Assess self-reported dissociation symptoms with the Dissociative Experiences Scale II (DES-II) at baseline and the primary endpoint.
- Assess self-reported posttraumatic growth with the Posttraumatic Growth Inventory (PTGI) at baseline and the primary endpoint.

The following objectives will compare effects in specified subjects:

- Assess PTSD symptoms via CAPS and PDS, depression symptoms via BDI-II, global functioning via GAF, sleep quality via PSQI, posttraumatic growth via PTGI, and dissociation symptoms via the DES-II, throughout Stage 2 in comparison to Stage 1 in crossover subjects.
- Assess long-term effects of MDMA-assisted psychotherapy on symptoms of PTSD, depression, and global function, sleep quality, dissociation symptoms via CAPS and PDS, BDI-II, GAF, PSQI, PTGI (in reference to start of the study), and DES-II one year after the final experimental session for each subject.

The following objectives will include exploratory analyses intended to inform future protocol design:

- Explore the effects of each experimental session upon self-reported changes in consciousness, as those associated with a transformational or mystical experience via the States of Consciousness Questionnaire (SOCQ).
- Assess the effect of the third experimental session for active dose subjects in Stage 1 and Stage 2 using CAPS, PDS, BDI-II, GAF, PSQI, PTGI (in reference to start of the study), and DES-II.
- Assess the ability of the investigators and subjects to accurately guess treatment group assignment in Stage 1.
- Correlate adherence to the treatment manual with Global CAPS scores using adherence criteria ratings to assess videos of psychotherapy sessions.

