9.9.1 Primary Efficacy Analyses

Clinician Administered PTSD Scale-4 (CAPS-4)

The primary efficacy evaluation is the change from baseline to the primary outcome timepoint (visit 12) in the CAPS-4 Global Severity score of PTSD (difference score). The primary efficacy comparison will be made with ANOVA at an alpha level of 0.05. If the primary hypothesis rejects, pairwise comparisons among the treatment groups will be made with t-tests. If the parametric assumptions for the ANOVA and t-test analyses are not met, the analogous nonparametric methods will be used (Kruskall-Wallis, Wilcoxon Rank-Sum).

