The sponsor will collect ratings of adherence to the treatment manual from specifically selected types of sessions. Descriptive statistics will be computed for each adherence scale within a given session. If sufficient data is available, the sponsor will correlate the mean adherence ratings for adherence scale and session type with Global CAPS scores from the closest available endpoint assessment to investigate the effects of adherence to the treatment manual on reduction in PTSD symptoms. If it is found that there are specific factors within the adherence scales, then the factor will be correlated with Global CAPS score.

Qualitative Interviews

Qualitative interviews conducted by a researcher who is part of the study team during the 12-month follow-up visit will be transcribed to text. A computer-assisted qualitative data analysis software package will be utilized to assist in thematic content analysis of the interview transcripts. A member of the research team will code the interviews for content, to identify emerging themes and organize data into thematic constructs utilizing a grounded theory approach. Descriptive statistics will be calculated for emerging themes.

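### The adherence analysis asks about reduction in PTSD symptoms but correlates adherence with an unadjusted CAPS score, so baseline severity could appear as an adherence effect

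*SAP*

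**What the plan says.** SAP 9.9.3.1, under adherence to the treatment manual, gives the purpose as "to investigate the effects of adherence to the treatment manual on reduction in PTSD symptoms". The planned calculation is that "the sponsor will correlate the mean adherence ratings for adherence scale and session type with Global CAPS scores from the closest available endpoint assessment". If factors are found within the adherence scales, "then the factor will be correlated with Global CAPS score". The analysis runs only if there are enough data.

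Protocol 12.0 pairs the same aim with the same variable and names no time point: mean ratings are correlated "with Global CAPS scores to investigate the effects of adherence to the treatment manual on reduction in PTSD symptoms". Protocol 5.1.3 gives the goal as to "correlate therapist adherence to the treatment manual with outcome". The objective in SAP 4.2, also in Protocol 3.2, is listed as exploratory: "Correlate adherence to the treatment manual with Global CAPS scores using adherence criteria ratings to assess videos of psychotherapy sessions".

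None of these places mentions a change score, a baseline covariate, or a dose term or stratum. Elsewhere the SAP says so when it means change. The primary variable in SAP 9.9.1 is "the change from baseline to the primary outcome timepoint (visit 12) in the CAPS-4 Global Severity score of PTSD (difference score"), and SAP 9.9.2 and 9.9.2.1 likewise speak of change from baseline, absolute changes or difference scores.

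**The concern.** The aim is a reduction and the variable is a level. A subject who falls from 110 to 60 and one who starts and stays at 60 contribute the same value. Entry requires a CAPS of at least 50 with no upper limit (Protocol 4.2.1), so baseline severity can vary and carry through into the endpoint score.

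The closest available endpoint may also be visit 12, 17, 27 or 32, depending on the session. These visits follow different numbers of sessions and different doses.

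This analysis links delivery of the therapy to outcome. Protocol 5.1.3 ties it to standardising the treatment, and Protocol 2.3 says the study will continue to refine the manual. A correlation that reflects who was less ill at entry would be a poor guide for either purpose.

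**Working it through.** **The plan's own figures.** None is given for this analysis. The only power figures, in Protocol 12.1, concern the primary comparison of 18 with 5. A two-sided 0.05 t-test gives 0.327 for an effect size of 0.8 (stated 0.33) and 0.546 for 1.1 (stated 0.55). They reproduce, but nothing below depends on them.

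**Inputs from the documents.** N = 26, allocated 12:9:5 (SAP 6.0); two-sided 0.05 (SAP 9.0). The SAP names no coefficient for this analysis; Pearson is used here.

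**Assumed inputs.** The correlation of adherence with baseline CAPS (r_AB) is taken as 0, -0.3 or -0.5, and that of baseline with endpoint CAPS (r_BE) as 0.3, 0.5 or 0.7. The standard deviation is the same at both visits. Adherence has no true effect.

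**Step 1, raw endpoint score.** The expected spurious correlation is r_AB × r_BE. For example, -0.3 × 0.5 = -0.15 and -0.5 × 0.7 = -0.35. The critical value at N = 26 is |r| = 0.39.

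**Step 2, change score without a baseline term.** With equal standard deviations the expected correlation is -r_AB × √((1 - r_BE)/2). For -0.3 and 0.5 this is 0.3 × √0.25 = +0.15, the same size as in step 1 with the sign reversed.

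**Step 3, false-positive rates.** Simulation with 2,000 trials per row. Each cell gives the mean r, then the share significant:

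| r_AB | r_BE | Raw endpoint | Change score | Endpoint given baseline and dose |
|---|---|---|---|---|
| -0.3 | 0.3 | -0.09, 8% | +0.18, 15% | 0.00, 5% |
| -0.3 | 0.5 | -0.15, 12% | +0.15, 12% | 0.00, 4% |
| -0.3 | 0.7 | -0.21, 19% | +0.11, 8% | -0.01, 5% |
| -0.5 | 0.3 | -0.15, 12% | +0.29, 33% | -0.01, 5% |
| -0.5 | 0.5 | -0.24, 23% | +0.25, 24% | 0.00, 5% |
| -0.5 | 0.7 | -0.34, 44% | +0.19, 16% | 0.00, 6% |

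Repeating the raw-score analysis at r_AB = -0.3 with 20,000 trials gave 7%, 11% and 18%; the differences are simulation error. With r_AB = 0, every method stays near 5%.

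**Step 4, dose.** Dose biases the result only if adherence ratings also differ by dose. With r_AB = 0, r_BE = 0.5, an adherence shift of 0.5 to 0.8 SD and a dose effect of 0.8 to 1.1 SD, the raw correlation averages -0.06 to -0.12 and is significant in 5% to 10% of trials. Adding baseline and dose group returns this to about 5%.

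**Step 5, lost precision.** Here baseline and change each have SD 20 and are independent given adherence, and adherence correlates -0.5 with change.
- Adherence unrelated to baseline: the correlation with the endpoint is -0.5 × 20/√(20² + 20²) = -0.35. Power is 44% on the raw endpoint and 77% on change.
- Adherence correlated +0.3 with baseline: the endpoint variance is 400 + 400 + 2 × 400 × (0.3 × -0.5) = 680, so the correlation is (0.3 - 0.5) × 20/√680 = -0.15. Power on the raw endpoint falls to about 12%.
- Endpoint adjusted for baseline and dose: power is 67% to 72% across the two settings.

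**The case against.** The strongest reply is that the analysis does what its objective says. The objective is to correlate adherence with Global CAPS scores, it is listed as exploratory, no efficacy conclusion depends on it, and SAP 9.0 allows further labelled post-hoc analyses. That lowers the severity. It does not remove the mismatch, because the SAP paragraph itself names reduction in symptoms as what is being investigated.

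The sample is also not assured. Ratings come from selected sessions and are guaranteed only for each therapist team (Protocol 5.1.3). With 12 rated subjects, the case that gives about 18% at 26 gives about 10%. This stands.

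Four stronger readings are tempting, and the documents do not support them:
- A reader might infer that milder subjects are easier to treat by the manual, so that a false adherence effect is to be expected. Neither document says so. The adherence-baseline correlation is an assumption throughout.
- A reader might infer that the SAP prescribes pooling across doses. It is silent; it simply gives no dose term or stratum.
- A reader might infer that the ratings capture the drug's effect on the subject. Protocol 5.2.3 describes what therapists do, such as supporting periods of inner focus, and the raters are blinded (Protocol 5.1.3). Confounding by dose is possible but not shown, and step 4 suggests that it would be modest.
- A reader might infer that a promised comparison of experienced and intern teams has been left out. Protocol 2.3 says only that "Information will be collected regarding consistency and response between the teams by reviewing adherence criteria in blinded videos of therapy sessions", and no objective in either document compares the teams. That is a separate, descriptive matter.

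**Conclusion.** The point holds as a mismatch between aim and variable in both documents, which no other section cures. Its effect is conditional. If adherence is related to baseline severity within the assumed ranges, the false-positive rate at N = 26 is about 7% to 44%. If it is unrelated, the rate stays near 5% and the harm is lost precision.

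A reader might infer that putting a change score in place of the endpoint score settles the matter. It does not. With equal standard deviations at the two visits, change is itself related to baseline, and under the same assumptions the change score is falsely positive in about 8% to 33% of trials, with the sign reversed. Adjusting the endpoint for baseline and dose group held 4% to 6% in every setting without a true effect.

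Severity is low, because the analysis is exploratory and conditional on sufficient data.

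**What to change.** In SAP 9.9.3.1, for both the scale-level and the factor-level analyses, replace the raw correlation with a partial correlation, or a regression, of endpoint Global CAPS on mean adherence rating, adjusted for baseline Global CAPS and Stage 1 dose group. Name one endpoint visit for each session type in place of the closest available one, and analyse Stage 1 and Stage 2 sessions separately. For Stage 2 sessions, the baseline is visit 12, or the repeated assessment where Protocol 5.2.9 requires one. All Stage 2 subjects come from the comparator group, so the dose term drops out there. With the five planned subjects, 5 - 2 - 1 = 2 residual degrees of freedom remain, so Stage 2 results should be descriptive.

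The change is wording only and uses data already planned. It costs three degrees of freedom in Stage 1, one for baseline and two for dose group: 24 become 21 at N = 26. If few subjects are rated, the SAP should allow adjustment for baseline alone. With 12 subjects, for example, that leaves 12 - 2 - 1 = 9 degrees of freedom, against 12 - 2 - 3 = 7 for the full adjustment.

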9.9.4 Safety Analyses

The primary measure of safety will be the reporting of adverse events. The Adverse events considered are Treatment Emergent Adverse Events (TEAE) defined as those AE's that occurred after dosing and existing medical history diagnoses that worsened during the study. Verbatim terms on case report forms will be mapped to preferred terms and system organ classes using the MedDRA dictionary. For incidence reporting if a subject has more than one AE mapped to the same preferred term, that AE will be reported only once using the highest severity and closest relationship to study drug. Subject incidence of AEs will be displayed by Stage I treatment group and by system organ class. AEs will also be summarized by severity and relationship to study drug. Subject incidence of SAEs by Stage I treatment group will also be displayed. In addition to the listing of all AEs, a listing of SAEs and a listing of AEs leading to discontinuation of study drug will be included.

Summary tables of frequency listings of commonly reported AEs (Spontaneously Reported Reactions) mapped to preferred terms will be displayed during and after each experimental session by Stage 1 treatment group.

Columbia Suicide Severity Rating Scale (C-SSRS)

Suicidal ideation and behavior will be summarized according to suggestions made in the Columbia-Suicide Severity Rating Scale Scoring and Data Analysis Guide [2]. A positive response for suicidal ideation is counted when a subject answers "yes" to any one of the five suicidal ideation questions (Categories 1-5) on the C-SSRS, i.e. a score > 0 for suicidal ideation score. Serious suicidal ideation is a suicidal ideation score of 4 or 5. A positive response for suicidal behavior occurs when a subject answers "yes" to any one of the five suicidal behavior questions (Categories 6-10) on the C-SSRS, i.e. a score > 0 for suicidal behavior score. The number and percent of positive responses of Positive Ideation, Serious Ideation, and Positive Behavior will be tabulated by Stage I treatment group and time period. Compare lifetime serious suicidal ideation and positive behavior frequencies to cumulative frequencies anytime during the study until end of Stage 1 and Stage2.

Subjective Units of Distress (SUD)

Descriptive statistics for SUD scores will be calculated by Stage 1 treatment group and time period with counts and percentages.

Visual analog scale for Tinnitus and/or Pain visual analog scale

Formal analysis of Changes in Tinnitus and/or Pain visual analog scale scores will only occur if three or more subjects complete Changes in Tinnitus and/or Pain visual analog scale at baseline and primary endpoint. Likewise, formal between-groups analyses will not be performed if all primary endpoint scores are from subjects assigned to the same treatment group. Descriptive statistics will be presented on the difference between baseline and primary endpoint changes in Tinnitus and/or Pain visual analog scale scores in the full dose and comparator dose treatment groups.

Vital signs

Vital signs (heart rate, body temperature, systolic and diastolic blood pressure) will be summarized using descriptive statistics at baseline and at each post-baseline time point. Occurrences of systolic and diastolic blood pressure, heart rate, and body temperature readings above the pre-determined cutoff will be displayed with numbers and percentages by timepoint.

Paced Auditory Serial Addition Test (PASAT) and Repeatable Battery for the Assessment of Neuropsychological Status (RBANS)

RBANS and PASAT scores at baseline and primary endpoint will be compared in each active dose group and comparator dose groups using descriptive statistics. In an exploratory analysis, the effects of maximal exposure to MDMA on neurocognitive function using the RBANS and PASAT will be examined.

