4.1 Planned Duration of Study and Visit Windows

Subjects enrolled in this study will fall into two categories that will determine the duration of the study. These include the follow-up portion of the study, which encompasses 12 months after the final experimental session.

- Active dose subjects completing Stage 1 only: 15 months.
- Comparator dose subjects who continue and complete Stage 2: 18 months.

Screening may take up to two months, with the baseline CAPS being conducted no more than 8 weeks before the first experimental session, leaving room for appropriate medication washout of at least five half-lives of pre-study psychiatric medications and active metabolites, and one additional week for stabilization. For example, the maximum washout would be seven weeks for subjects tapering off of fluoxetine plus one week for stabilization. Preparatory sessions should be scheduled approximately one week apart, with the first experimental session taking place three to five weeks after enrollment, and at most 8 weeks after the baseline CAPS. The maximum window from the start of screening to the first experimental session is 13 weeks. The optimal timing for Stage 2 is one month after the primary endpoint visit in Stage 1, with a maximum allowable window of five months. Any delay between visits would result in a corresponding extension of study duration.

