- Last-month CAPS to assess PTSD symptoms and eligibility, which may be recorded to video in as many instances as necessary to establish inter-rater reliability.
- GAF to assess general psychological function.
- PASAT to assess cognitive function.
- RBANS to assess cognitive function.

The subject will complete the following self-report measures:

- PTGI (in reference to time since the trauma)
- PDS to assess self-reported PTSD symptoms
- BDI-II to assess depression symptoms
- PSQI to assess sleep quality

- DES-II to assess dissociation symptoms

5.2.2 Preparatory Psychotherapy Sessions - Visits 1, 2, 3 (Stage 1), 18 (Stage 2)

Subjects who do not complete all screening activities will not be enrolled. Eligibility may be discussed by phone after screening is complete and at the time Visit 1 is scheduled but the final confirmation will occur at Visit 1. If all inclusion criteria and no exclusion criteria are met, eligibility will be confirmed with the subject.

- a. Complete a final review of Inclusion/exclusion criteria.
- b. Assess general wellbeing.
- c. Confirm eligibility and willingness to participate in study.
- d. Enroll subject and issue subject number.
- e. Ensure medical history and medication history is complete. After enrollment new events will be collected as AEs and new medications, as described in Sections 8.5 and 9.0.
- f. Discuss medication tapering, if applicable. Upon confirmation of eligibility, the study physician will consult the prescribing physician to initiate medication tapering for subjects who must refrain from taking a psychiatric medication for the study. Tapering will follow a time course appropriate for the medication given its half-life, with the first experimental session scheduled to occur after complete washout. Individuals using opiates for pain management will be asked to decrease the dose or avoid taking their pain medication for 24 hours prior to experimental sessions if possible, as these medications may reduce the efficacy of MDMA. Subjects will be permitted to take their prescribed opiate medication during this period if necessitated by pain flare-ups.

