8.5 Adverse Event Collection

The study physician will be responsible for reviewing and confirming all AEs and SAEs collected during the study. The therapists will collect AEs during study visits after enrollment.

All SAEs will be collected for the duration of the protocol. All SAEs which occur during the course of the trial, whether considered to be associated with the study drug or not, have to be reported within 24 hours of the investigator's awareness of their occurrence. All SAE reports should be faxed to the Sponsor. A fax number will be provided to the site in separate site-specific instruction for SAE reporting. In addition to the fax, the study physician, Clinical Investigator (CI), or designee should call the CRA during normal working hours and verbally inform the CRA of the SAE. During off business hours or if medical advice is needed immediately please call the Sponsor Medical Monitor. An SAE reporting instruction with all contact numbers will be provided to the site prior to study start.

Medical Monitor:

[name]
Email: [contact]
[contact]
[contact]

Study Monitor contact information will be provided in a separate contact list.

Adverse events that will be collected for the duration of the protocol are:

- All SAEs will be collected through subject termination.
- All AEs and spontaneously reported reactions will be collected on the day of drug administration and for seven days after each experimental session.
- Any spontaneously reported reactions that have not resolved to the subject's baseline level of severity after seven days will be collected on the Adverse Event Report page until resolution.
- Events requiring medical attention will be collected from enrollment through the subject's last two-month follow-up.
- Events related to planned treatments or physician visits for baseline conditions collected in the Medical History will not be collected unless there is an exacerbation of the condition.
- Any Adverse Event leading to withdrawal from the protocol will be collected throughout the study.
- All AEs related to changes in psychiatric status will be collected throughout the study.

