9.0 Concomitant Medications and Tapering Instructions

The study physician will record concomitant medications during screening. If the subject is being treated with psychiatric drugs at the time he or she is recruited into the study, the prospective subject will be encouraged to discuss medication tapering with his or her outside treating physician, if any, and will be required to give the study physician and PI permission to do so as well. The drugs will then be tapered in an appropriate fashion to avoid withdrawal effects. They will be discontinued long enough before the first experimental session to avoid the possibility of any drug-drug interaction (the interval will be at least five times the particular drug and active metabolites' half-life, plus one week for stabilization).

The therapists will request information about any changes in medication just prior to each experimental session. The study physician will be responsible for reviewing and confirming all medications collected during the study.

All medications, over the counter (OTC) and prescription will be collected from screening through seven days after the last MDMA session. From seven days after the last MDMA session through study termination only prescription or OTC medications taken to treat AEs will be collected. Throughout the protocol all medications used to treat AEs will be collected, as described in Section 8.5, and all changes including discontinuations or additions to psychiatric medications will be collected. Medications will be recorded on the concomitant medications CRF.

Subjects must be willing to refrain from taking any psychiatric medications during Stage 1 and Stage 2, with the exception of gabapentin when prescribed for pain control. If the subject is on stimulants for ADHD at baseline, they can continue to use them at the same dose and frequency as long as they discontinue five half-lives before each experimental session and do not restart for ten days after each experimental session. Individuals using opiates for pain management will be asked to decrease the dose or avoid taking their pain medication for 24 hours prior to experimental sessions if possible, as these medications may reduce the efficacy of MDMA. Subjects will be permitted to take their prescribed opiate medication during this period if necessitated by pain flare-ups.

Table 6. Medication Tapering Table

Generic Name	Brand Name	Half-life (hours) Including Active Metabolites	Days for Washout

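### The second part of the TEAE definition in SAP 9.9.4 is not tied to first dose, so a listed diagnosis that worsens during the pre-dose medication taper can be tabulated as treatment-emergent

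*SAP*

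**What the plan says.** SAP 9.9.4 makes AE reporting the primary measure of safety and defines a treatment-emergent AE in two parts. New events are "defined as those AE's that occurred after dosing". To these it adds "existing medical history diagnoses that worsened during the study". Incidence is shown by Stage 1 treatment group and system organ class, and AEs are also summarised by severity and relationship. A subject with several AEs under one preferred term is counted once, at the highest severity and the closest relationship.

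The protocol sets the timeline. Enrollment takes place at Visit 1 (Protocol 5.2.2), and from then "After enrollment new events will be collected as AEs and new medications", subject to the collection rules in 8.5. The taper also starts on study: "Upon confirmation of eligibility, the study physician will consult the prescribing physician to initiate medication tapering", "with the first experimental session scheduled to occur after complete washout". Protocol 4.1 gives the gap, "with the first experimental session taking place three to five weeks after enrollment". Protocol 8.5 states that "All AEs related to changes in psychiatric status will be collected throughout the study".

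**The concern.** The two parts of the definition use different clocks. A new event must follow dosing. Worsening of a diagnosis already in the history need only fall within the study, and the study includes several weeks before any MDMA is given. In those weeks some subjects stop psychiatric medication, which is when an existing psychiatric diagnosis might be expected to worsen.

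At stake is how the main safety tables are read. An event that began before any exposure would be shown as treatment-emergent under a particular MDMA dose. It would be a psychiatric event, the kind this trial most needs to place correctly in time, and in arms this small a single subject is visible.

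**Working it through.** The plan states no figure on this point, so the check is of wording and timeline, followed by simple arithmetic.

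**1. Does anything else tie the second part to dosing?** The phrase about dosing sits in the clause on new AEs. The second part has its own clause and its own time window. No other section of the SAP or protocol limits it.

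**2. Is there an on-study interval before dosing in which the taper occurs?** Protocol Table 2 ticks medication taper under Visits 1 to 3. Protocol 4.1 puts the first session 3 to 5 weeks after enrollment, or 21 to 35 days. Protocol 9.0 sets the drug-free period: "the interval will be at least five times the particular drug and active metabolites' half-life, plus one week for stabilization". From the washout days in Protocol Table 6, plus 7 days:

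- sertraline: 6 + 7 = 13 days
- citalopram: 8 + 7 = 15 days
- diazepam: 15 + 7 = 22 days
- aripiprazole: 16 + 7 = 23 days
- fluoxetine: 45 + 7 = 52 days

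Before any time for dose reduction is added, the first two fit inside 21 to 35 days. Diazepam and aripiprazole fit if the gap is at least 22 or 23 days. Fluoxetine does not fit. The interval at issue is therefore a matter of weeks.

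**3. Would worsening in that interval be recorded?** Protocol 8.1 includes exacerbation of a pre-existing condition in the AE definition. Protocol 8.5 collects all AEs only on dosing days and for seven days after, and the all-AEs row of Table 2 is blank for Visits 1 to 3. What is collected before dosing is SAEs, events requiring medical attention, AEs leading to withdrawal, and AEs of psychiatric status. The last of these is ticked at Visits 1 to 3.

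**4. Which events meet the second part before dosing?** All three conditions are needed:

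- the diagnosis is in the medical history
- its worsening is recorded under one of the categories in step 3, in practice mainly psychiatric status
- the subject later receives study treatment, because SAP 9.1 limits the Safety population to treated subjects

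**5. How far can one subject move a table?** SAP 6.0 gives planned arms of 12 (125 mg), 9 (100 mg) and 5 (40 mg), 26 in all. For one preferred term, one subject adds at most 1/n:

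- 1/12 = 8.3 points
- 1/9 = 11.1 points
- 1/5 = 20 points

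SAP 9.3 also places two replaced subjects in the Safety population, and their arms are not stated. If both were in the same arm, the figures for that arm would be 1/14 = 7.1, 1/11 = 9.1 or 1/7 = 14.3 points. The shift is zero if the subject also has a post-dose event counted under the same term.

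**6. What does the once-per-term rule do?** As an illustration, suppose a subject has a severe, Not Related worsening in the taper and a mild, Probably Related event after dosing, both under one preferred term. Taking the highest severity and the closest relationship gives a single entry: severe, Probably Related. Neither event was that.

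**The case against.** The strongest reply is that this is loose drafting. The sentence defines treatment-emergent events and opens with dosing, so the authors may have meant the second part to cover worsening on treatment. SAP 9.2 already uses the first dose date as a reference when it imputes partial AE start dates. That may well be the intent, but it is not the text, and a programmer could code it either way.

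Several mitigations also stand. Protocol 8.1 grades an AE Not Related if exposure has not occurred, so the relationship table partly separates these events; overall incidence and severity do not. SAP 9.9.4 plans no inferential test on AE incidence, and the full AE listing would show the events, though not as a separate group.

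A reader might infer that any anxiety or insomnia on stopping a drug would count. The documents do not support this: a new symptom with no listed diagnosis fails the second part, and before dosing it fails the first.

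A reader might also infer a bias for or against a dose. Protocol 5.2.3 and 5.3 place randomization at least 24 hours before the experimental session, so taper events would normally come before it and should fall across arms by chance. Protocol 4.0 and SAP 5.0 speak of assignment upon enrollment, and these passages need to be reconciled. Even then subjects and therapists are blinded, so systematic bias does not follow.

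Finally, anxiety, insomnia and low mood are on the reaction list in Protocol 8.2, and Protocol 7.2 includes anxiety and insomnia among reactions reported by 40% to 80% of subjects in both MP-1 conditions. If such reactions are counted under the same preferred term, the shift in incidence could often be zero, leaving only the severity effect.

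**Conclusion.** The point holds as a defect of definition. Followed literally, SAP 9.9.4 puts recorded pre-dose worsening of a listed diagnosis into the TEAE incidence and severity tables by dose group, for subjects later dosed. The consequence is inflated and blurred incidence, and possible merging of a taper event's severity with a post-dose event's attribution. It is not systematic bias between arms.

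The size is at most about 8, 11 or 20 points per affected subject per term on the planned arms, somewhat less in any arm that holds a replaced subject, and zero where a post-dose event already counts under that term. The total effect cannot be estimated: the documents do not say how many subjects taper, how many worsen, or how many such changes would be recorded as AEs. The conclusion assumes that the definition is programmed as written and that randomization follows the taper.

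**What to change.** In SAP 9.9.4, change the second part to existing medical history diagnoses that worsened after the first MDMA dose. Classify by the date of AE onset or worsening against the first dose date, and judge worsening against the latest pre-dose AE or medical-history record. Visit 4 should not be named as the reference, because Table 2 schedules no severity grade for existing diagnoses at that visit. Apply the once-per-term rule only to events that are treatment-emergent under the revised wording. List AEs from enrollment to first dose separately as pre-treatment events.

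There is a precedent in the plan: SAP 9.5 already takes the C-SSRS baseline after enrollment and before drug.

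The cost is one phrase and one extra listing, using dates and records already collected. One limit remains. Under SAP 9.2, a start date with the day missing, in the month of first dose, is set to the first dose date, so a taper event dated that way could still be classed as treatment-emergent. Such cases should be flagged in the listing.
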